Prespecified high ($\geq 75\%$ increase from baseline) SHBG group (biomarker for MGL-3196 hepatic levels) showed similarly enhanced improvement in MRI-PDFF and liver enzymes relative to placebo. Overall safety has been good with mostly mild AEs and some moderate AEs which are generally balanced between placebo and treatment group. There have been 3 SAEs, blinded to treatment code, none of which are considered related to study drug by independent Medical Monitor ([REDACTED]) or Sponsor. More than 30 patients have now had a follow up 36 week liver biopsy; although the NASH scoring is blinded, study pathologist, [REDACTED], who reads the 36 week biopsies on an ongoing basis, has not reported any findings of non-NASH or biliary lesions (Page 2 of scoring sheet “Any non-NASH findings” is not blinded).

Table 1. Results of Week 12 Primary Endpoint Analysis

	ALL MGL-3196	High MGL-3196 ¹	Low MGL-3196	Placebo
Number of patients	[REDACTED]	[REDACTED]	[REDACTED]	[REDACTED]
Primary Endpoint:				
Relative change in MRI-PDFF (% change from baseline, median)				
Significance relative to placebo	[REDACTED]	[REDACTED]	[REDACTED]	[REDACTED]
Percentage of patients attaining $\geq 30\%$ liver fat reduction	[REDACTED]	[REDACTED]	[REDACTED]	[REDACTED]
Significance relative to placebo	[REDACTED]	[REDACTED]	[REDACTED]	[REDACTED]

¹ Prespecified MGL-3196 exposure groups ≥ 2700 ng*hr/ml and < 2700 ng*hr/ml

MGL-3196-05 Amendment 6 adds a minor dose adjustment (increase in dose of 20-25%) in a small percentage (~10) of patients still completing the 36 week Main study, who have low exposure on doses of 60-80 mg (low predose exposure, low SHBG response).

[REDACTED]
Several parameters and visits were assessed to assure that the data were not impacted by compliance issues (e.g. not taking drug the day before visit, taking drug prior to visit).

[REDACTED] SHBG levels (blinded to patient ID) were reviewed because SHBG has a long half-life, and may be a marker for average drug exposure. Any dose adjustments will be made by unblinded personnel.

In patients remaining in the Main study or randomized to MGL-3196 who meet criteria and consent to Extension study:

Table 2. Doses in Main and Extension Study in Patients Assigned to MGL-3196 in the Main Study

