9 SAFETY ASSESSMENTS

9.1 Adverse Events

An adverse event is defined as any untoward medical occurrence in a clinical investigation patient administered a pharmaceutical product, which does not necessarily have a causal relationship with this treatment. An adverse event can therefore be any unfavorable and/or unintended sign (including an abnormal laboratory finding), symptom, or disease temporally associated with the use of an investigational medicinal product, whether or not related to the investigational medicinal product. All adverse events, including observed or volunteered problems, complaints, or symptoms, are to be recorded on the appropriate eCRF.

Adverse events, which include clinical laboratory test variables, will be monitored and documented from the time of informed consent until study participation is complete. Patients should be instructed to report any adverse event that they experience to the Investigator. Beginning at the Screening Visit, investigators should make an assessment for adverse events at each visit and record the event on the appropriate adverse event eCRF.

Wherever possible, a specific disease or syndrome rather than individual associated signs and symptoms should be identified by the Investigator and recorded on the eCRF. However, if an observed or reported sign or symptom is not considered a component of a specific disease or syndrome by the Investigator, it should be recorded as a separate adverse event on the eCRF. Additionally, the condition that led to a medical or surgical procedure (eg, surgery, endoscopy, tooth extraction, or transfusion) should be recorded as an adverse event, not the procedure.

Any medical condition already present at screening should not be reported as an adverse event unless the medical condition or signs or symptoms present at baseline change in severity or seriousness at any time during the study. In this case, it should be reported as an adverse event.

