9.1.3 Assessment of Adverse Events by the Investigator

The Investigator will assess the severity (intensity) of each adverse event as mild, moderate, or severe, and will also categorize each adverse event as to its potential relationship to study drug using the categories of yes/no.

9.1.3.1 Assessment of severity:

Mild – An event that is easily tolerated and generally not interfering with normal daily activities.

Moderate – An event that is sufficiently discomforting to interfere with normal daily activities.

Severe – An event that is incapacitating with inability to work or perform normal daily activities.

9.1.3.2 Causality assessment:

The relationship of an adverse event to the administration of the study drug is to be assessed according to the following definitions:

No (unrelated, not related, no relation) – The time course between the administration of study drug and the occurrence or worsening of the adverse event rules out a causal relationship and another cause (concomitant drugs, therapies, complications, etc.) is suspected.

Yes (related) – The time course between the administration of study drug and the occurrence or worsening of the adverse event is consistent with a causal relationship and no other cause (concomitant drugs, therapies, complications, etc.) can be identified.

The definition implies a reasonable possibility of a causal relationship between the event and the study drug. This means that there are facts (evidence) or arguments to suggest a causal relationship.

The following factors should also be considered:

- The temporal sequence from study drug administration-
 - The event should occur after the study drug is given. The length of time from study drug exposure to event should be evaluated in the clinical context of the event.
- Underlying, concomitant, intercurrent diseases-
 - Each report should be evaluated in the context of the natural history and course of the disease being treated and any other disease the patient may have.
- Concomitant drugs-
 - The other drugs the patient is taking or the treatment the patient receives should be examined to determine whether any of them might be recognized to cause the event in question.
- Known response pattern for this class of study drug-
 - Clinical and/or preclinical data may indicate whether a particular response is likely to be a class effect.
- Exposure to physical and/or mental stresses-

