10.2.2 Analysis of Safety

The safety endpoints for this study include: adverse events, safety laboratory assessments, vital signs, 12-lead ECGs, concomitant medications, and clinical assessments.

The adverse events will be coded using the latest version of the Medical Dictionary for Regulatory Activities (MedDRA). Treatment-emergent adverse events (TEAEs) will be defined as adverse events that are new or worsening after the first dose of study drug. A general summary of patients with TEAEs and SAEs will be tabulated with numbers and percentages of patients, and repeated for severity and relationship to study drug per treatment group. The number of adverse events leading to withdrawal and SAEs leading to death will also be summarized. The incidence of TEAEs will be summarized by body system and treatment group.

The safety laboratory data will be summarized by visit and by treatment group, along with changes from the baseline. The values that are <LLN or >ULN of the reference range will be flagged. Those values or changes in values that are identified as being clinically significant will be flagged. Laboratory abnormalities of special interest will be summarized.

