### **3.8.1 Adverse Events**

A Treatment-Emergent Adverse Event (TEAE) is defined as any AE that occurred for the first time after the first dose of double-blind study drug or existed prior to the first dose and worsened during the post dosing period. AE worsening applies to severity, or relationship to study drug.

A summary overview of TEAEs will be provided, which presents the number and percentage of patients in each treatment group from the Safety Population for the 12-week Treatment Period and the whole 36-week Treatment Period satisfying each of the following categories:

- Any TEAEs,
- Maximum severity of TEAEs,
- Study drug-related TEAEs,
- Maximum severity of study drug-related TEAEs,
- All TE-SAEs,
- All study drug-related TE-SAEs,
- TEAEs leading to death,
- TEAEs leading to study drug discontinuation, and
- Study drug-related TEAEs leading to interruption/study drug discontinuation.

Adverse events will be coded using MedDRA. The number and percentage of patients with TEAEs will be summarized by their MedDRA preferred term within system organ class and by treatment. AEs will be counted by the number of events as well as the number of patients. For event count summaries, multiple AE events with the same MedDRA coded terms (preferred term and system organ class) and onset date and time from the same patient will only be counted once. For patient count summaries, multiple AE events with the same MedDRA coded terms (preferred term and system organ class) from the same patient will only be counted once. Whether the AE belongs to the 12-week Treatment Period and the whole 36-week Treatment Period will be determined by the AE onset date.

The number and percentage of patients with TEAEs will be summarized by reported maximum severity within each MedDRA preferred term within system organ class and by treatment.

The number and percentage of patients with any TE-SAEs, drug-related TEAEs, drug-related TE-SAEs, and TEAEs and TE-SAEs that lead to study drug discontinuation will be summarized by preferred term within system organ class and by treatment. In these summaries, any patients reporting multiple episodes of the same TEAE (i.e., same preferred term and system organ class) will be counted once.

All SAEs will be listed with an indication of whether the SAE was treatment emergent or started prior to treatment.

All TEAEs that are reported as having led to a withdrawal of study drug will be listed.

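### SAP 3.8.1 leaves seriousness out of its definition of worsening, so a pre-dose adverse event that first turns serious after dosing, at unchanged severity and relationship, misses the by-arm TE-SAE tables

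*SAP*

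**What the plan says.** SAP 3.8.1 gives two routes to treatment emergence. An event qualifies if it first occurs after the first dose of double-blind drug, or if it "existed prior to the first dose and worsened during the post dosing period". The next sentence limits the second route: "AE worsening applies to severity, or relationship to study drug".

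Protocol 9.1 says a condition already present at screening is not an adverse event "unless the medical condition or signs or symptoms present at baseline change in severity or seriousness at any time during the study"; if it does change in that way, it is to be reported as one. Protocol 10.2.2 defines TEAEs as "adverse events that are new or worsening after the first dose of study drug" and does not say which dimension must worsen. Adverse events are "monitored and documented from the time of informed consent until study participation is complete" (Protocol 9.1), so some can have an onset before the first dose.

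The tabulations by arm in SAP 3.8.1 are all of treatment-emergent events. They include TE-SAEs (overview and by preferred term) and TEAEs leading to death. Events are allotted to the 12-week and 36-week periods by onset date. Separately, every SAE is listed, with a flag showing whether it was treatment-emergent or began before treatment.

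**The concern.** The protocol grades severity and seriousness separately. Severity (9.1.3.1) is intensity on three steps, ending at severe: "An event that is incapacitating with inability to work or perform normal daily activities". Seriousness (9.2) depends on outcome, such as death, threat to life or hospitalisation. A patient can be admitted to hospital, or die, with no change in the recorded severity grade. An event already graded severe has no higher grade to move to.

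A change in relationship will seldom fill the gap. Under Protocol 9.1.3.2 an event is called related only if its timing fits and no other cause can be identified, and the investigator is told that the event should follow drug administration. An event that began before dosing will rarely switch to related on those terms.

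At stake is the comparison of serious events by arm. A listing records the event but does not compare arms, and when SAEs are few one misclassified event shows in the percentages.

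**Working it through.** The plan gives no figure for this point, and a definition has nothing to recompute. The check sets the texts side by side and classifies each type of event under the SAP's literal wording.

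**Can a pre-dose event exist here?** Yes. Collection begins at consent, screening lasts up to 42 days (Protocol 3.1.1), and screening may include a liver biopsy (Protocol 6.2 and 9.15).

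**Classification of an event that first becomes serious after dosing**

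- (a) Onset after the first dose: a TEAE by the first route, so it is counted as a TE-SAE.
- (b) Onset before the first dose, with severity or relationship also worsening: a TEAE by the second route, so it meets the definition.
- (c) Condition present at screening, severity and relationship unchanged: Protocol 9.1 requires it to be reported as an adverse event. It is counted if that report is a new record with post-dose onset, and not counted if it is handled as pre-existing. The SAP does not say which.
- (d) Adverse event with onset between consent and first dose, severity and relationship unchanged: it fails both routes. It is not a TEAE, so it cannot be a TE-SAE or, if fatal, a TEAE leading to death. It stays in the SAE listing.

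So case (d) drops out by the stated rule, and case (c) depends on data handling.

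**A linked problem with dates.** Because periods are assigned by onset date, a pre-dose event that does qualify through worsening, as in (b), has an onset before both treatment periods. Read literally, it may be placed in neither. The listing flag also offers treatment-emergent and started-before-treatment as alternatives, although a worsened pre-dose SAE is both.

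**Scale of one event.** Inputs: Safety Population of 84 on MGL-3196 and 41 on placebo (overview of TEAEs in the Amendment 6 summary).

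- MGL-3196: 1/84 = 1.2 percentage points.
- Placebo: 1/41 = 2.4 percentage points.

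For context, the Amendment 6 summary states: "There have been 3 SAEs, blinded to treatment code". That is a mid-study count. It does not say when any of the three events began, so it gives no estimate of how many events the rule would affect.

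**The case against.** A reader might infer that any event turning serious after dosing is lost. The documents do not support that. Cases (a) and (b) both meet the TEAE definition.

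The strongest counter-argument concerns case (c). Until a screening condition changes, it is medical history and not an adverse event. When it turns serious, Protocol 9.1 has the site report an adverse event, and that event can fairly be said to occur for the first time after dosing. The worsening sentence is then never reached, and the protocol governs collection while the SAP governs classification. This is a plausible reading and it narrows the point. It does not settle it, because the SAP never states how such a record is dated, and it does not touch case (d).

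It can also be said that case (d) is rare. It needs onset in a short screening window and later seriousness with neither severity nor relationship changing. The variant that is already severe needs a patient randomised while incapacitated, whom the investigator could exclude under exclusion criterion 28. That stands as an argument about frequency.

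Nor is any serious event hidden. All SAEs are listed, and Protocol 10.2.2 calls for a summary of SAEs and of SAEs leading to death without limiting either to treatment-emergent events. That stands too. But the SAP carries those summaries out only for treatment-emergent events, so the protocol's broader wording shows a further place where the SAP is narrower and does not restore the missing by-arm count.

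Finally, a reader might take the three SAEs to mean that a third of serious events could be missing. Nothing in the documents shows that any of the three began before dosing.

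**Conclusion.** The point holds in a limited form. SAP 3.8.1 is narrower than Protocol 9.1 and gives no reason for it. An adverse event with onset between consent and first dose that becomes serious or fatal after dosing, at the same severity and relationship, is excluded from the by-arm TE-SAE and TEAE-death tables. A screening condition is excluded in the same way only if it is handled as pre-existing.

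The number of such events is not given and is probably small. The 1.2 and 2.4 points show what a single event would do to an arm's percentage and are not an estimate of bias. The conclusion assumes that the SAP sentence is programmed as written and that the site does not open a new record with a post-dose onset when the event turns serious.

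**What to change.** Change the sentence in SAP 3.8.1 to: *AE worsening applies to severity, seriousness, or relationship to study drug.* Add two rules:

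1. Any adverse event that first meets a seriousness criterion, including death, on or after the first dose is treatment-emergent and is counted as a TE-SAE.
2. A pre-dose event that worsens, including a screening condition reported under Protocol 9.1, is assigned to the 12- and 36-week periods by its date of worsening and not by its onset date.

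The second rule is needed because adding seriousness alone could still leave the event outside both periods. The SAE listing flag should also allow an event to be both pre-dose in onset and treatment-emergent.

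The cost is a few lines of SAP text and a small change in programming. The TE-SAE count may rise slightly. The date on which seriousness was first met must be available or derived; the protocol describes submission of the SAE form but not its date fields, so this should be checked before the rule is programmed.

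### SAP 3.8.1 assigns adverse events to the 12-week and 36-week overviews by onset date, which can leave out pre-dose events that worsen on treatment and, because the period end is unclear, events seen at the Week 38 follow-up

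*SAP*

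**What the plan says.** SAP 3.8.1 has two routes to treatment-emergent status: a first occurrence after the first dose, or an event that "existed prior to the first dose and worsened during the post dosing period". It adds that "AE worsening applies to severity, or relationship to study drug". Protocol 10.2.2 agrees in substance, defining these as "adverse events that are new or worsening after the first dose of study drug". Neither definition gives an end date.

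The SAP overview table is presented "for the 12-week Treatment Period and the whole 36-week Treatment Period satisfying each of the following categories", and one of its rows is "Maximum severity of TEAEs". The period rule is: "Whether the AE belongs to the 12-week Treatment Period and the whole 36-week Treatment Period will be determined by the AE onset date". No other date is used.

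On collection, Protocol 9.1 says that adverse events "will be monitored and documented from the time of informed consent until study participation is complete", so events starting during screening are recorded. A condition already present at screening is not to be reported "unless the medical condition or signs or symptoms present at baseline change in severity or seriousness at any time during the study". The Protocol does not say which onset date such a report should carry.

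**The concern.** The definition and the period rule do not fit together. The definition deliberately admits events that precede dosing and then worsen; the period rule looks only at when an event began, and such events began before either period opened. Safety after 12 and 36 weeks is a secondary objective (Protocol 2.2, SAP 2.1.2), and these overviews are the tables that report adverse events by those two periods. As written, they can omit one of the event types that the plan's own definition was meant to capture.

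The second gap is at the other end. If the 36-week period stops at Week 36, an event that starts in follow-up and is reviewed at the Week 38 visit is treatment-emergent but has no period. The Week 36 biopsy may be done up to 3 days after the visit (Protocol 6.4.10), so a biopsy complication could start in that interval.

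**Working it through.** The plan states no figure to reproduce. The check applies the SAP 3.8.1 rules literally to constructed events.

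**Inputs**
- Screening: up to 42 days (Protocol 3.1.1).
- Week 12 = Day 84, Week 36 = Day 252, Week 38 follow-up = Day 266 (Protocol 6.4.5, 6.4.10, 6.5).
- SAE reporting: to 30 days after the last dose (Protocol 9.3.1.1). With a last dose on Day 252, that is 252 + 30 = Day 282.
- End of the 36-week period: SAP 3.6 runs it through Week 36 for compliance and starts its next exposure category at Day 253. The heading of Protocol 6.4 runs the main-study treatment period to Week 38.

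**Rule.** An event is in the 12-week overview if its assigned date lies in Days 1 to 84, and in the 36-week overview if it lies in Days 1 to 252 (or 1 to 266 under the Protocol heading). All six events below are treatment-emergent by definition.

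| Event | By onset, end Day 252 | By onset, end Day 266 | By date it became treatment-emergent, end Day 252 |
|---|---|---|---|
| New, Day 50 | both | both | both |
| Onset Day -20, worsens Day 30 | neither | neither | both |
| Onset Day -20, worsens Day 200 | neither | neither | 36-week only |
| Onset Day 50, worsens Day 200, one record | both | both | both |
| Onset Day 260 | neither | 36-week only | neither |
| SAE, onset Day 275 | neither | neither | neither |

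**Reading the table**
1. Rows 2 and 3 are the main defect. Moving the end of the period does not help; changing the date used does.
2. Row 4 is in the correct periods, but its severity is open. If the worsening stays on the one record, nothing in SAP 3.8.1 stops the Day 200 severity from appearing in the 12-week row. If the worsening opens a new record, that record falls only in the 36-week overview and the problem does not arise.
3. Row 5 turns entirely on where the period ends. The interval at issue is 266 - 252 = 14 days.
4. Row 6 lies outside both overviews on every reading. It would still appear in the SAE listing that SAP 3.8.1 provides.

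**The case against.** The strongest reply is that the data may never take the problematic form. Protocol 9.1 has a condition reported as an adverse event when its severity changes from baseline. If sites enter that report with the date of change, the onset-date rule places it correctly. The duplicate rule in SAP 3.8.1, which merges events only when coded term and onset date and time all match, is compatible with that practice. This stands as a possibility, but neither document requires it. The Protocol rule is framed around conditions already present at screening; whether it also covers events that start between consent and Day 1 is arguable.

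A second reply is that the Protocol 6.4 heading already brings follow-up into the treatment period. It might, but SAP 3.6 points the other way, so the period end still has to be stated.

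Three stronger readings are tempting and are not supported:
- A reader might infer that these events vanish from the safety analysis. They do not. The preferred-term tables in SAP 3.8.1 are not expressly limited to the two periods, all SAEs and all treatment-emergent events leading to withdrawal of study drug are listed, and SAP 5 lists all available data.
- A reader might infer that late worsening is always credited to Week 12. That follows only if worsening is kept on the original record and severity is not capped.
- A reader might scale by days, such as 42/252 = 16.7% for screening or 14/266 = 5.3% for follow-up, and call the result the share of events missing. That needs a constant onset rate and, for screening events, a worsening fraction. The documents give neither. The overview also counts patients, so someone with another in-period event still counts under any event.

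**Conclusion.** The point holds in limited form. Unless worsening is entered as a new record, the onset-date rule leaves a treatment-emergent event with pre-dose onset in neither overview. Events starting in Days 253 to 266 are also in neither if the SAP 3.6 usage governs, and in the 36-week overview if the Protocol 6.4 heading does.

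The effect is confined to the period-specific summaries. The number of events or patients affected cannot be computed from the documents. The same rule applies to both arms, nothing in the documents shows a bias between them, and no hypothesis test on these tables is planned. It is a minor correction, worth making because it brings the overviews into line with the plan's own definition and its 12-week and 36-week safety objective.

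**What to change.** Amend SAP 3.8.1 in three places.

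(a) Assign the period by the date the event became treatment-emergent: the onset date if that is on or after the first dose, otherwise the date of first post-dose worsening. The worsening date should be used only for pre-dose onsets. Taking the later of onset and worsening for every event would move the Day 50 event that worsens on Day 200 out of the 12-week overview, although it began on treatment.

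(b) Where worsening is kept on the original record, use for the 12-week overview the maximum severity reached by Week 12.

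(c) State that the 36-week overview runs from the first dose through the Week 38 follow-up visit and ends before the first extension dose. The stop matters because Extension Day 1 may coincide with Week 38 (Protocol 6.7.1), when former placebo patients begin active drug. SAEs after Week 38 remain in the SAE listing.

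The cost is a few sentences and a small programming change. The downside is that worsening dates must be taken from the severity-change records wherever the worsening was not entered as a new event. Because the SAP also counts a change in relationship to study drug as worsening, the date for that case needs stating too.
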